8.2.2 Secondary Objectives

- To describe long-term safety data, for at least 5 years after the end of Increlex® therapy, in children and adolescents who have received Increlex® therapy, regardless of treatment duration and adult height;
- To describe long-term safety data at 2 and 5 years after the end of Increlex® therapy, for a subset of children and adolescents who have been exposed to Increlex® therapy for at least 3 cumulative years excluding interruptions, regardless of adult height;
- To describe Increlex® effectiveness throughout the study until the participant reaches adult height;
- To identify predictive factors of the main effectiveness parameters by modelisation of height velocity, FAH, height SDS change, timing and progression of puberty, bone age development;
- To evaluate Increlex® therapy exposure (dose and treatment duration) and compliance;
- To determine the lowest effective dose of Increlex® defined as the cut-off dose under which there is no further effect on the height velocity anymore (short-term evaluation: 1-year height velocity);
- To assess QoL during Increlex® therapy and in the post-treatment period (using EQ-5D version EQ-5D-Y (paediatric questionnaire));
- To describe the timeframe of the occurrence of neoplasia (benign and malignant) and hypoglycaemia.

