9 RESEARCH METHODS

9.1 Registry Design

This is a multicentre, global, prospective, non-interventional, observational, open-ended, post-authorisation safety surveillance registry designed to collect safety and effectiveness data on the use of Increlex® in children and adolescents with SPIGFD. Data on treatment exposure, compliance and QoL of participants will also be collected.

The objective is to screen all Increlex®-treated patients with SPIGFD at each participating site of the participating countries with the aim of enrolling as many patients as possible.

The decision to prescribe Increlex® will be made prior to and independently of the decision to enrol the patient in the registry. Treatment with Increlex® should be directed by physicians who are experienced in the diagnosis and management of patients with growth disorders. The dose should be individualised for each participant according to the locally approved product information. The data collected for a participant will be those that exist in their medical records as part of standard medical care except for additional QoL assessments and post-treatment safety follow-up in the context of fulfilling the Specific Obligation (SO2). Data will be collected utilising an electronic Case Report Form (eCRF) via the internet.

The date of the inclusion visit is not determined by the protocol. Patients who have started Increlex® treatment before the implementation of the registry in their country may also be enrolled. Data will be then retrospectively collected in the eCRF.

During the first visit, the Investigator will check the patient's eligibility according to the inclusion and exclusion criteria and must obtain written informed consent before any further data collection.

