Effectiveness analyses will be based on the Registry Population.

The raw values of the following effectiveness parameters will be described at different timepoints (every 6 months from the start of treatment) as well as the change from baseline: height SDS, height velocity, BMI SDS, bone age development, pubertal stage.

For participants who reached the FAH, the estimation of the difference between the PAH and the FAH will be presented.

Main effectiveness parameters (height SDS, height velocity) will be described according to average dose received over the course of the study and according to dose ranges (e.g. 4 dose ranges (≤ 50 , $]50-80]$, $]80-110]$, $> 110 \mu\text{g/kg BID}$)). This analysis will support the description of the lowest effective dose.

Multivariate linear regression analyses will be used to identify predictive factors of height SDS change, height velocity, bone age development after 1 year of treatment or more. The same method will be used to assess the predictive factors of FAH.

The Cox regression model including covariates as sex, age or height SDS at start of Increlex® will be used to estimate the time from start of treatment to reach the puberty for a subset of prepubertal patients at start of Increlex®.

Biological assessments (IGF-1, IGFBP3), raw values and change from baseline, will be described at different timepoints.

Exposure to Increlex® Therapy

The treatment duration as well as the dose of Increlex® at each timepoint (initiation, 3 months, 6 months, 1 year, and every 6 months thereafter) will be described.

Duration of post-treatment follow-up will also be summarised.

Quality of Life Analysis

The QoL of participants aged 4 and over will be assessed using the EQ-5D-Y paediatric questionnaire (see Section 9.3.2.5 for details).

The 5 dimensions/domains (mobility; looking after myself; doing usual activities; having pain or discomfort; feeling worried, sad or unhappy) will be described at each timepoint as well as the evolution from baseline. The VAS will be described as a quantitative parameter at each timepoint as well as the change from baseline.

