7.2 Does the protocol address:				
7.2.1. Selection biases (e.g. healthy user bias)				N/A
7.2.2. Information biases (e.g. misclassification of exposure and endpoints, time-related bias)				N/A
7.3 Does the protocol address the validity of the study covariates?				N/A
Comments: Confounding and covariates do not apply to this study.				

Section 8: Effect modification	Yes	No	N/A	Section Number
8.1 Does the protocol address effect modifiers? (e.g. collection of data on known effect modifiers, sub-group analyses, anticipated direction of effect)				N/A
Comments: Effect modifiers are not applicable to this study.				

Section 9: Data sources	Yes	No	N/A	Section Number
9.1 Does the protocol describe the data source(s) used in the study for the ascertainment of:				
9.1.1 Exposure? (e.g. pharmacy dispensing, general practice prescribing, claims data, self-report, face-to-face interview, etc.)				9.4, 9.8.3
9.1.2 Outcomes? (e.g. clinical records, laboratory markers or values, claims data, self-report, subject interview including scales and questionnaires, vital statistics, etc.)				9.4, 9.8.3
9.1.3 Covariates?				N/A
9.2 Does the protocol describe the information available from the data source(s) on:				
9.2.1 Exposure? (e.g. date of dispensing, drug quantity, dose, number of days of supply prescription, daily dosage, prescriber)				9.3, 9.8.3
9.2.2 Outcomes? (e.g. date of occurrence, multiple event, severity measures related to event)				9.3, 9.8.3
9.2.3 Covariates? (e.g. age, sex, clinical and drug use history, co-morbidity, co-medications, lifestyle, etc.)				N/A
9.3 Is a coding system described for:				

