Comments: An independent Data Monitoring Committee composed of external experts (paediatric endocrinologists) will be asked to conduct periodic reviews of available safety data on at least an annual basis.				

Section 12: Limitations	Yes	No	N/A	Section Number
12.1 Does the protocol discuss the impact on the study results of:				
12.1.1 Selection bias?				9.9
12.1.2 Information bias?				9.9
12.1.3 Residual/unmeasured confounding? (e.g. anticipated direction and magnitude of such biases, validation sub-study, use of validation and external data, analytical methods)				N/A
12.2 Does the protocol discuss study feasibility? (e.g. study size, anticipated exposure, duration of follow-up in a cohort study, subject recruitment)				9.5
Comments: Confounding does not apply to this study.				

Section 13: Ethical issues	Yes	No	N/A	Section Number
13.1 Have requirements of Ethics Committee/ Institutional Review Board been described?				9.11, 11.4
13.2 Has any outcome of an ethical review procedure been addressed?				N/A
13.3 Have data protection requirements been described?				10.2
Comments:				

Section 14: Amendments and deviations	Yes	No	N/A	Section Number
14.1 Does the protocol include a section to document amendments and deviations?				5
Comments:				

Section 15: Plans for communication of study results	Yes	No	N/A	Section Number
15.1 Are plans described for communicating study results (e.g. to regulatory authorities)?				12
15.2 Are plans described for disseminating study results externally, including publication?				12
Comments:				

Name of the main author of the protocol:

Date: / /

Signature: _____

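### The lowest-effective-dose objective rests on an unadjusted comparison across individualised doses, while Appendix 2 declares confounding inapplicable

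*Protocol*

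**What the plan says.** Section 8.2.2 sets this secondary objective: "To determine the lowest effective dose of Increlex® defined as the cut-off dose under which there is no further effect on the height velocity anymore". The outcome is 1-year height velocity.

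Section 9.1 says how dose arises: "The dose should be individualised for each participant according to the locally approved product information". Sections 9.2.7.2 and 9.3.2.4 add that dose changes and their reasons are recorded during treatment. Eligible children are 2 to 18 years old (9.2.1).

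One analysis is tied to the objective, in 9.7.2.6 and in near-identical terms in 9.3.1.2: "Main effectiveness parameters (height SDS, height velocity) will be described according to average dose received over the course of the study and according to dose" bands, of which four are given as an example. Its stated role is this: "This analysis will support the description of the lowest effective dose". No adjustment is named.

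Elsewhere, 9.7.2.6 plans:
- change from baseline in height SDS and height velocity, by 6-monthly timepoint;
- multivariable linear regression to find predictors of height velocity and height SDS change after 1 year or more, with predictors not listed;
- a Cox model for time to puberty with sex, age or height SDS at start as covariates.

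In the Appendix 2 checklist, the comment to Section 7 (Bias) reads "Confounding and covariates do not apply to this study" and the comment to Section 12 (Limitations) reads "Confounding does not apply to this study". Items 7.1, 7.1.1, 10.4 and 12.1.3, on confounding and its adjustment, are marked not applicable.

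Section 9.9 concedes that the design is non-randomised and without fixed dose, that the lowest effective dose may not be determinable, and that some pre-treatment growth measures will be missing.

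**The concern.** A cut-off below which a drug has no effect is a statement about effect across doses. Reading it from group means requires groups that are alike apart from dose. Here the dose follows the child, and growth velocity between 2 and 18 years depends on age, puberty and severity of disease. Raw means by dose range therefore mix the effect of dose with the characteristics of the children in each range. This remains true if dose is restricted to the first year, so it is separate from the choice of averaging window.

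The checklist makes matters worse. It tells whoever writes the analysis plan that there is nothing to adjust for, although the protocol body uses covariates and names the lack of randomisation as a limitation.

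The stake is real even for a secondary objective. Section 7.2 links neoplasia risk particularly to off-label use and to doses above the maximum tolerated, so a misleading lowest effective dose would bear on the benefit-risk reading.

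**Working it through.** The protocol states no sample size, power or effect size for this objective, so there is no figure to reproduce. The check has two parts.

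**1. Passages side by side.**
- 8.2.2 asks for a dose effect; 9.1 makes dose depend on the child; 9.3.1.2 and 9.7.2.6 answer with an unadjusted description.
- Appendix 2 says covariates do not apply; 9.7.2.6 names covariates for the Cox model and plans a multivariable regression; 9.7.2.5 explores adverse events against age, pubertal status and dose.
- Appendix 2 marks residual confounding not applicable; 9.9 says the non-randomised design without fixed dose puts the objective in doubt.

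**2. How large an artefact could be, with a true dose effect of zero.**

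Inputs from section 7.2 (pivotal study): height velocity 2.6 (SD 1.7) cm/year before treatment and 8.0 (SD 2.3) cm/year at year 1. Mean gain: 8.0 − 2.6 = 5.4 cm/year.

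Assumptions, not in the documents:
- joint normality;
- four equal-sized dose groups in place of the four example ranges;
- correlation of dose with pre-treatment velocity, *rd*, from −0.2 to −0.6;
- correlation of pre-treatment with year-1 velocity, *rp*, from 0.2 to 0.6.

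The mean of a standard normal variable in its top quarter is 1.271, so the top and bottom groups differ by 2 × 1.271 = 2.542 SD of dose. Then:
- false gap in raw year-1 velocity = 2.542 × *rd* × *rp* × 2.3
- false gap in change from pre-treatment = 2.542 × *rd* × (*rp* × 2.3 − 1.7)

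| *rd* | *rp* | Raw gap (cm/year) | Change-score gap (cm/year) |
|---|---|---|---|
| −0.2 | 0.2 | −0.23 | +0.63 |
| −0.2 | 0.6 | −0.70 | +0.16 |
| −0.4 | 0.4 | −0.94 | +0.79 |
| −0.6 | 0.2 | −0.70 | +1.89 |
| −0.6 | 0.6 | −2.10 | +0.49 |

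Worked example, last row: 2.542 × (−0.6) × 0.6 × 2.3 = −2.10, and 2.542 × (−0.6) × (1.38 − 1.7) = +0.49.

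A simulation of 2,000,000 children per setting agreed with these formulas to within 0.01. In the same simulation, regression of year-1 velocity on dose and pre-treatment velocity returned a dose gap within 0.01 of zero. That holds because pre-treatment velocity is the only confounder in the model.

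Three results follow:
- the raw gap runs from 0.23 to 2.10 cm/year in size, or 4% (0.23/5.4) to 39% (2.10/5.4) of the pivotal-study gain;
- in this range a change score does not remove the false gap but reverses its sign (+0.16 to +1.89);
- if *rd* were positive, all signs would flip.

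**The case against.** The best defence has four parts.

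*The limitation is disclosed and the aim is modest.* Section 9.9 is candid, the dose analysis only supports a description, and 9.7.2.1 calls all analyses primarily descriptive. This stands as a reason for moderate severity. Disclosure does not supply adjustment, though, and it makes the checklist statement harder to defend.

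*Covariates belong in the SAP.* The SAP is a separate document that has not been seen, and the log for Amendment 8 records an SAP update. A missing covariate list would indeed be no finding. But the protocol itself ties the objective to an unadjusted description and marks adjustment not applicable.

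*Some control is already there.* Height SDS is a standardised score, a regression for height velocity is planned, and 9.7.3 allows subgroups by Laron syndrome, pubertal status or sex. All true, but the objective is defined on height velocity, and none of these is linked to the dose cut-off.

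*The checklist is only a supporting document.* It says so itself. It is still part of the protocol and contradicts the body.

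A reader might infer that the plan ignores each child's pre-treatment growth altogether. It does not: change from baseline is planned by timepoint for both parameters. It is simply not linked to the dose-range description.

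**Conclusion.** The point holds as a contradiction within the protocol and as a weak analysis for a stated objective. Followed as written, the plan yields dose-range means that can differ because of who received which dose. Under the assumptions shown, the artefact could be about 0.2 to 2.1 cm/year between extreme groups, against a gain of 5.4 cm/year. These are illustrations; actual size and direction cannot be known from the documents.

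Two stronger readings are tempting and unsupported:
- *That the lowest effective dose will be biased downward.* This needs poorer growers to be moved to higher doses. The protocol says doses are individualised and adjusted, not in which direction.
- *That modest selection produces a very large false gap.* Applying a correlation of −0.3 directly to year-1 velocity gives 2.542 × 2.3 × (−0.3) = −1.75 cm/year, 32% of the gain. If −0.3 is instead the correlation of dose with growth potential, and potential correlates only 0.2 to 0.6 with the outcome, the gap is −0.35 to −1.05 cm/year. The documents give neither correlation.

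The objective is secondary and the limitation partly disclosed, so this should be changed but does not threaten the primary safety analysis.

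**What to change.** In sections 9.3.1.2 and 9.7.2.6:
- Make the analysis supporting this objective the linear regression of 1-year height velocity already planned, with dose as a term and adjustment for age, sex, pubertal stage and height SDS at start of treatment, Laron syndrome (yes/no) and, where available, pre-treatment height velocity.
- Report adjusted means per dose range with 95% confidence intervals beside the raw description.
- Show change from pre-treatment velocity as descriptive only, not as the control for confounding.
- State that the result is exploratory and that residual confounding remains, including dose changes made in response to growth on treatment, which baseline adjustment cannot remove.

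In Appendix 2, correct items 7.1, 7.1.1, 7.3, 9.1.3, 9.2.3, 9.3.3 (the covariates row), 10.4 and 12.1.3, with their comments, so that they agree with 9.7.2.6 and 9.9.

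Cost: wording in two sections and the checklist, and one extra table from variables the registry already collects. Participants without a pre-treatment velocity, whom 9.9 expects, drop out of the fully adjusted model or need a second model without that term.
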